Clinical Trial Protocol

Document Number:		c27981303-05
BI Trial No.	1368-0043	
BI Investigational Medicinal Product	BI 655130 (Spesolimab)	
Title	An open-label phase I trial to assess pharmacokinetics and safety of single subcutaneous doses and single intravenous doses of BI 655130 in healthy Chinese male and female subjects (single doses, open-label study in parallel-group design).	
Lay Title	A trial in healthy Chinese volunteers to test how different doses of BI 655130 are taken up in the body.	
Clinical Phase	I	
Trial Clinical Leader	 Phone: [REDACTED] Fax: [REDACTED]	
Principal Investigator	 Phone: [REDACTED] Fax: [REDACTED]	
Status	Final Protocol (Revised Protocol (based on global amendment 04))	
Version and Date	Version: 5.0	Date: 26 Feb 2021
Page 1 of 76		
Proprietary confidential information © 2021 Boehringer Ingelheim International GmbH or one or more of its affiliated companies. All rights reserved. This document may not - in full or in part - be passed on, reproduced, published or otherwise used without prior written permission		

Proprietary confidential information © 2021 Boehringer Ingelheim International GmbH or one or more of its affiliated companies

CLINICAL TRIAL PROTOCOL SYNOPSIS

Company name	Boehringer Ingelheim (BI)
Protocol date	29 Jul 2019
Revision date	26 Feb 2021
BI trial number	1368-0043
Title of trial	An open-label phase I trial to assess pharmacokinetics and safety of single subcutaneous doses and single intravenous doses of BI 655130 in healthy Chinese male and female subjects (single doses, open-label study in parallel-group design).
Principal Investigator	[REDACTED]
Trial site	[REDACTED] Phone: [REDACTED] Fax: [REDACTED] Email: [REDACTED]
Clinical phase	I
Trial rationale	To investigate the PK and safety of spesolimab in Chinese healthy subjects
Trial objectives	To investigate PK, including dose proportionality, following single SC and IV doses of spesolimab in healthy Chinese subjects
Trial endpoints	Primary endpoint AUC _{0-∞} and C _{max} of spesolimab Secondary endpoints: The occurrence of treatment-emergent adverse events (AEs) The occurrence of drug-related AEs
Trial design	Open-label without placebo, parallel-group design

Proprietary confidential information © 2021 Boehringer Ingelheim International GmbH or one or more of its affiliated companies

Number of subjects	Up to 60 subjects including up to 10 subjects for replacement of early discontinuation
total entered	
each treatment	10 per dose group
Diagnosis	Not applicable
Main criteria for inclusion	Healthy male or female subjects (at least three subjects for each gender within each dose group) Age of 18 to 45 years (inclusive) Body weight \geq 50 kg for male and \geq 45 kg for female Body mass index (BMI) \geq 19 and $<$ 26 kg/m ² for male and female at visit 1
Test product 1	BI 655130 (60 mg/mL) solution for infusion
dose	Single dose of 450 mg, 900 mg and 1200 mg
mode of admin	IV as 90 min infusion
Test product 2	BI 655130 (150 mg/mL) solution for injection
dose	Single dose of 300 mg and 600 mg
mode of admin	SC injection
Comparator product	Not applicable
dose	Not applicable
mode of admin	Not applicable
Duration of treatment	One day (single dose) for each treatment
Statistical methods	Descriptive statistics will be calculated for all endpoints. Dose proportionality of Spesolimab will be explored using a regression model for AUC _{0-∞} and C _{max} for IV doses. A 90% confidence interval (CI) for the slope will be computed.

FLOW CHART S.C.

Single dose group for SC

Single dose of Spesolimab as 300 mg and 600 mg SC (subjects will receive only one dose)

Visit	Day	Time relative to first drug administration (planned time) [h:min]	Approx. time (actual time) [h:min]	Event and comment	PK _{blood} ⁴	Plasma ADA ⁸	Laboratory ³	Body weight	12-lead ECG	Vital signs (BP, PR, RR, body temperature) ¹⁰	Query on AEs, concomitant therapies ¹¹
1	-28 to -3			screening ¹			X ¹⁴	X	X	X	
	-2	-48:00	8:00	ambulatory visit			X ¹³				X ¹³
2	-1	-12:00	20:00	admission to trial site			X ⁹				X
1	1	-2:00	6:30		X ²	X ²	X ^{2,14}		X ²	X ²	X ^{2,5}
		0:00	8:00	drug administration							
		0:10	8:10							X	
		0:30	8:30		X				X	X	X ⁵
		1:00	9:00							X	
		1:30	9:30						X	X	
		2:00	10:00	light breakfast ⁶	X				X	X	
		3:00	11:00		X					X	
		4:00	12:00	lunch ⁶	X					X	X ⁵
		6:00	14:00						X	X	
		8:00	16:00		X					X	
		10:00	18:00	dinner ⁶							
		12:00	20:00		X				X	X	X ⁵
2	2	24:00	8:00	breakfast ⁶	X				X	X	X ⁵
		28:00	12:00	lunch ⁶							
		32:00	16:00							X	
		34:00	18:00	dinner ⁶							X ⁵
3	48:00	8:00		breakfast ⁶ discharge from trial site (confirmation of fitness) ⁷	X				X	X	X ⁵
4	72:00	8:00		ambulatory visit	X		X				X ⁵
5	96:00	8:00		ambulatory visit	X						X ⁵
6	120:00	8:00		ambulatory visit	X						X ⁵
7	144:00	8:00		ambulatory visit	X						X ⁵
8	168:00	8:00		ambulatory visit	X		X		X	X	X ⁵
15	336:00	8:00		ambulatory visit	X	X					X ⁵
22	504:00	8:00		ambulatory visit	X		X		X	X	X
29	672:00	8:00		ambulatory visit	X	X	X		X	X	X ⁵
36	840:00	8:00		ambulatory visit	X						X
43	1008:00	8:00		ambulatory visit	X	X					X
57	1344:00	8:00		ambulatory visit	X	X					X ⁵
71	1680:00	8:00		ambulatory visit	X	X					X
92 ±2	2184:00	8:00		ambulatory visit	X	X	X ¹⁴				X
120 ±3	2856:00	8:00		ambulatory visit	X	X					X
148 ±3	3528:00	8:00		ambulatory visit	X	X					X
3	176 ±3	4200:00	8:00	EoTrial ¹²	X	X	X ¹⁴	X	X	X	X ⁵

Proprietary confidential information © 2021 Boehringer Ingelheim International GmbH or one or more of its affiliated companies

1. Screening with subject information, informed consent as the first measure, includes physical examination, check of vital signs including temperature, respiratory rate (RR), systolic and diastolic blood pressure (BP) and pulse rate (PR), 12-lead electrocardiogram (ECG), safety laboratory parameters (under fasting conditions), pregnancy test, drug screening, alcohol breath test, demographics (including determination of body height and weight, smoking and alcohol history), relevant medical history, concomitant therapy and review of inclusion/exclusion criteria.
2. The time is approximate; procedures are to be performed and completed within three hours prior to drug administration. Within three hours prior to the planned dosing, planned time -2:00 will be used.
3. Safety laboratory parameters include clinical chemistry, haematology, coagulation and urinalysis; in addition at screening: serology (hepatitis B virus [HBV], hepatitis C virus [HCV], human immunodeficiency virus [HIV], tuberculosis (QuantiFERON TB test), Follicle-stimulating hormone (FSH) and estradiol evaluation in questionable cases for determining postmenopausal status), and drug screening.
4. PK sampling times may be adapted based on information obtained during trial conduct.
5. Standardised assessment of local tolerability using the criteria swelling, induration, heat, redness, pain or other findings.
6. If several actions are indicated at the same time point, the intake of meals will be the last action.
7. Confirmation of fitness includes physical examination.
8. ADAs will be taken at baseline, Day 15, Day 29, Day 43, Day 57, Day 71, Day 92, Day 120, Day 148 and Day 176.
9. Only drug screening and alcohol breath test.
10. Evaluate vital signs at baseline, 10 minutes after and 1 hour post infusion/injection and in case of suspicion of hypersensitivity reaction including anaphylactic reaction.
11. AEs and concomitant therapies will be recorded throughout the trial, but will be specifically asked for at the time points indicated in the Flow Chart above.
12. EoTrial (end of trial) examination includes physical examination, body weight, vital signs, 12-lead ECG, safety laboratory parameters, recording of AEs and concomitant therapies. EoTrial to be performed not before last PK and ADA sampling.
13. Safety laboratory parameters are to be taken within two days prior to trial medication administration under fasting conditions and can be omitted if the screening examination is performed between Day -5 and Day -3. Also the AEs and concomitant therapies will be queried on Day -1.
14. At these time points, a urine pregnancy test will be done for female subjects.

FLOW CHART I.V.

Single dose group for IV

Single dose of Spesolimab as 450 mg, 900 mg and 1200 mg IV. (Subjects will receive only one dose)

Visit	Day	Time relative to first drug administration (planned time) [h:min]	Approx. time (actual time) [h:min]	Event and comment	PK _{blood} ⁴	Plasma ADA ⁸	Laboratory ³	Body weight	12-lead ECG	Vital signs (BP, PR, RR, body temperature) ¹¹	Query on AEs, concomitant therapies ¹²
1	-28 to -3			screening ¹			X ¹⁵	X	X	X	
	-2	-48:00	8:00	ambulatory visit			X ¹⁴				X ¹⁴
2	-1	-12:00	20:00	admission to trial site			X ¹⁰				X
	1	-2:00	6:30		X ²	X ²	X ^{2,15}		X ²	X ²	X ^{2,5}
		0:00	8:00	drug administration start of infusion							
		0:10	8:10							X	
		0:30	8:30						X	X	X ⁵
		1:00	9:00							X	
		1:30	9:30	▼ end of infusion ⁹	X				X	X	
		2:00	10:00	light breakfast ⁶	X				X	X	
		3:00	11:00		X					X	
		4:00	12:00	lunch ⁶	X					X	X ⁵
		6:00	14:00						X	X	
		8:00	16:00		X					X	
		10:00	18:00	dinner ⁶							
		12:00	20:00		X				X	X	X ⁵
	2	24:00	8:00	breakfast ⁶	X				X	X	X ⁵
		28:00	12:00	lunch ⁶							
		32:00	16:00							X	
		34:00	18:00	dinner ⁶							X ⁵
	3	48:00	8:00	breakfast ⁶ discharge from trial site (confirmation of fitness) ⁷	X				X	X	X ⁵
	4	72:00	8:00	ambulatory visit	X		X				X ⁵
	5	96:00	8:00	ambulatory visit	X						X ⁵
	6	120:00	8:00	ambulatory visit	X						X ⁵
	7	144:00	8:00	ambulatory visit	X						X ⁵
	8	168:00	8:00	ambulatory visit	X		X		X	X	X ⁵
	15	336:00	8:00	ambulatory visit	X	X					X ⁵
	22	504:00	8:00	ambulatory visit	X		X		X	X	X
	29	672:00	8:00	ambulatory visit	X	X	X		X	X	X ⁵
	36	840:00	8:00	ambulatory visit	X						X
	43	1008:00	8:00	ambulatory visit	X	X					X
	57	1344:00	8:00	ambulatory visit	X	X					X ⁵
	71	1680:00	8:00	ambulatory visit	X	X					X
	92 ±2	2184:00	8:00	ambulatory visit	X	X	X ¹⁵				X
	120 ±3	2856:00	8:00	ambulatory visit	X	X					X
	148 ±3	3528:00	8:00	ambulatory visit	X	X					X
3	176 ±3	4200:00	8:00	EoTrial ¹³	X	X	X ¹⁵	X	X	X	X ⁵

Proprietary confidential information © 2021 Boehringer Ingelheim International GmbH or one or more of its affiliated companies

1. Screening with subject information, informed consent as the first measure, includes physical examination, check of vital signs including temperature, RR, systolic and diastolic BP and PR, 12-lead ECG, safety laboratory parameters (under fasting conditions), pregnancy test, drug screening, demographics (including determination of body height and weight, smoking and alcohol history), relevant medical history, concomitant therapy and review of inclusion/exclusion criteria.
2. The time is approximate; procedures are to be performed and completed within three hours prior to drug administration. Within three hours prior to the planned dosing, planned time -2:00 will be used.
3. Laboratory tests (safety laboratory parameters) include clinical chemistry, haematology, coagulation and urinalysis; in addition at screening: serology (HBV, HCV, HIV, QuantiFERON TB test, FSH and estradiol evaluation in questionable cases for determining postmenopausal status), and drug screening.
4. PK sampling times may be adapted based on information obtained during trial conduct.
5. Standardised assessment of local tolerability using the criteria swelling, induration, heat, redness, pain or other findings.
6. If several actions are indicated at the same time point, the intake of meals will be the last action.
7. Confirmation of fitness includes physical examination.
8. ADA samples will be taken at baseline, Day 15, Day 29, Day 43, Day 57, Day 71, Day 92, Day 120, Day 148 and Day 176 (EoTrial).
9. First measure after completion of infusion collection of PK sample.
10. Only drug screening and alcohol breath test.
11. Evaluate vital signs at baseline, 10 minutes after and 1hour post infusion/injection and in case of suspicion of hypersensitivity reaction including anaphylactic reaction.
12. AEs and concomitant therapies will be recorded throughout the trial, but will be specifically asked for at the time points indicated in the Flow Chart above.

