Overall, multiple IV doses of 3 mg/kg, 6 mg/kg, and 10 mg/kg, as well as single and multiple doses of 20 mg/kg Spesolimab were found to be safe and well tolerated by the subjects in this trial. The incidences of drug-related AEs were balanced across treatment groups up to 10 mg/kg dose, while higher incidences were reported in the 20 mg/kg dose group. All AEs were of mild or moderate intensity. No dose-dependent AEs or other clinically relevant changes in safety laboratory parameters, vital signs, or 12-lead ECG were observed.

The relative bioavailability trial 1368-0003 explores PK as well as safety and tolerability of an SC formulation of Spesolimab at two different dose strengths of 150 mg (1 mL) and 300 mg (2 mL) in an open-label, sequential group design. In addition, the trial determines the relative bioavailability of the 300 mg SC dose (test group) compared to one single 300 mg IV dose of Spesolimab (reference group). The trial has been conducted in 36 healthy male and female subjects with 12 subjects per dose group. Local tolerability of the SC formulation was as well tolerated. Following an SC injection of 150 mg of Spesolimab, there were two cases of redness and one case of swelling at the injection site in 12 subjects. For the 300 mg SC dose there was one further report of redness in 12 subjects dosed. All local events were of mild intensity, occurred within 30 minutes after injection and completely resolved within 4 hours. There were no reports of injection site pain. The type, intensity and duration of systemic AEs were similar

Proprietary confidential information © 2021 Boehringer Ingelheim International GmbH or one or more of its affiliated companies

to what has been observed in the preceding single-rising dose / multiple rising dose studies 1368-0001 and 1368-0002. Most of the AEs were of mild intensity, there were no AEs considered to be dose limiting, and no SAEs.

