4.1.4 Drug assignment and administration of doses for each subject

The treatments to be evaluated are outlined in Table 4.1.4: 1. Each subject will receive one single dose of trial medication. For further details concerning timing see [Flow Chart](#). Detailed instructions for the preparation are provided in ISF.

Table 4.1.4: 1 Final dose of BI 655130 in solution containing active drug

Dose group	Final dose of BI 655130 [mg]
1	450 mg (IV infusion)
2	900 mg (IV infusion)
3	1200 mg (IV infusion)
4	300 mg (SC injection)
5	600 mg (SC injection)

For intravenous administration

Administration of trial medication will be performed after subjects have fasted overnight; fasting is to start no later than 10 h before the scheduled dosing. The detailed instructions for the dilution of the trial medication, the preparation of the infusion solution and the volume to be administered is provided in ISF. In all subjects, the infusion solution will be intravenously administered over 90 minutes approximately between 8:00 and 10:00 of the respective trial day. Start and end time of the infusion will be recorded.

In case of safety concerns, e.g. due to infusion reactions, the investigator or his/her designee should stop of the infusion. Based on his medical judgment, he/she will provide medications such as steroids, etc. as needed.

For administration of the infusion, an IV indwelling catheter is placed into an arm vein of the subject for saline infusion. A second indwelling catheter used for collection of blood samples will be placed on the contralateral arm.

The administration of the trial medication on all trial days will be done under supervision of the investigating physician or a designee. The so-called four-eye principle (two-person rule) should be applied for administration of trial medication and – if applicable – its preparation (e.g. reconstitution), if correct dosage cannot be ensured otherwise.

Water is allowed except for one hour before start of infusion and 1.5 hours after end of infusion.

For subcutaneous administration

Administration of trial medication will be performed after subjects have fasted overnight; fasting is to start no later than 10 h before the scheduled dosing. Trial medication will be injected subcutaneously in the abdominal region. The skin is sanitised before injection. Needle is placed subcutaneously and solution with trial medication is injected within 60 seconds. Detailed handling instructions will be provided in the ISF.

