7.8.5 Others

Physical examination

Physical examination findings, including general appearance, neck, lungs, cardiovascular system, abdomen, extremities, and skin will be reported as relevant medical history/baseline condition (i.e., a condition already existent before intake of study drug) or as AE and will be summarised as such.

No separate listing or analysis of physical examination findings will be prepared.

Local tolerability

[figure not shown]
Local tolerability will be assessed by the investigator on the basis of 'swelling', 'induration', 'heat', 'redness', 'pain', or 'other findings'. A frequency table with worst assessment by treatment group and in total will be provided.

Body weight

Body weight will be determined at screening and end of trial visit. Descriptive statistics including change from baseline will be performed by treatment group and in total.

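### Flow Chart I.V. schedules no AE query or standardised site check between 0:30, mid-infusion, and 4:00, 2.5 hours after the infusion ends, so short infusion-site reactions may not reach the local tolerability table

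*Protocol*

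**What the plan says.** The protocol synopsis gives the IV doses as "IV as 90 min infusion". In Flow Chart I.V. the 0:00 row is "drug administration start of infusion" and the 1:30 row is marked "end of infusion". For SC, Protocol 4.1.4 says that the "solution with trial medication is injected within 60 seconds".

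In both charts the last column holds the query on AEs and concomitant therapies. Where a mark carries footnote 5, it also calls for a "Standardised assessment of local tolerability using the criteria swelling, induration, heat, redness, pain or other findings". Through Day 3 these footnoted marks are identical in the two charts: -2:00, 0:30, 4:00, 12:00, 24:00, 34:00 and 48:00.

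SAP 7.8.5 says of local tolerability: "A frequency table with worst assessment by treatment group and in total will be provided".

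Protocol 1.2.5 describes local reactions to SC doses in the earlier relative bioavailability trial. All were mild; they "occurred within 30 minutes after injection and completely resolved within 4 hours".

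**The concern.** The same clock times mean different things for the two routes. For SC, the 0:30 check looks at the site half an hour after the whole dose is in. For IV, it looks at the site while two thirds of the infusion is still to come, and the next structured look is well after it has finished.

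The structured assessment is what SAP 7.8.5 summarises as the worst finding. If it is never scheduled at or soon after full delivery, a brief reaction can come and go between two checks and the IV frequency errs low. The IV and SC frequencies also come from checks at different distances from the end of dosing. All 30 planned IV subjects (3 groups of 10) share this schedule.

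Protocol 1.4 itself lists local bruising, inflammation and pain among the risks of either route, so the site check has a purpose in the IV groups too.

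**Working it through.** **1. End of infusion.** 0:00 + 90 min = 1:30, which agrees with the chart.

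**2. What Flow Chart I.V. schedules around the gap.**

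| Time | PK | ECG | Vital signs | AE query + footnote 5 |
|---|---|---|---|---|
| 0:30 | – | X | X | X |
| 1:00 | – | – | X | – |
| 1:30 (infusion ends) | X | X | X | – |
| 2:00 | X | X | X | – |
| 3:00 | X | – | X | – |
| 4:00 | X | – | X | X |

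**3. Size of the gap.**
- Position of the first check: 30 / 90 = one third of the infusion time.
- Gap: 4:00 − 0:30 = 3.5 h.
- Infusion time inside the gap: 60 / 90 = 67%.
- Next check after infusion end: 4:00 − 1:30 = 2.5 h.

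**4. First two checks relative to the end of dosing.**
- SC (injection over by 0:01): 0:30 − 0:01 = +29 min; 4:00 − 0:01 = +3 h 59 min.
- IV: 0:30 − 1:30 = −1 h; 4:00 − 1:30 = +2.5 h.

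**5. What the scheduled checks can catch.** Two assumptions are needed: onset is uniform over the 30 minutes after dosing ends, and the check records what is present at that moment (the documents state no recall period). The documents give no duration for IV-site reactions, so the duration d is varied.

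IV: onset lies between 1:30 and 2:00, so the wait to the 4:00 check is 2.0 to 2.5 h. The share caught is 0 for d ≤ 2 h, (d − 2) / 0.5 between 2 and 2.5 h, and 1 from 2.5 h upwards. At d = 2.25 h it is 0.25 / 0.5 = 50%.

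SC: onset lies between minute 1 and minute 31, and the check is at minute 30. For d from 0.5 to 3 h the share caught is 29 / 30 = 97%.

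**6. What one added IV mark does.**
- At 2:00: for onset between 1:30 and 2:00 the wait becomes 0 to 0.5 h, so every such reaction lasting 0.5 h or more is caught.
- At 1:30: for onset between 0:30 and 1:30 the wait falls from 2.5–3.5 h to 0–1 h. It adds nothing for onset after 1:30.
- At both: the longest interval without a check between 0:30 and 4:00 falls from 3.5 h to 2.0 h (2:00 to 4:00).

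**7. PK was re-timed for the route; the site check was not.** The SC chart has a PK sample at 0:30. The IV chart has none there and places one at 1:30 instead. The footnote 5 marks did not change.

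**The case against.** The strongest reply is that subjects are far from unobserved in these 3.5 hours. Vital signs are scheduled at four times, PK at three and ECG at two. IV footnote 12 has AEs recorded throughout. Protocol 5.2.6.2.1 requires spontaneous reporting and treats the charted questions as a minimum. Protocol 1.4 promises close in-house observation and hypersensitivity monitoring during and after dosing. The 4:00 query can also bring out something that began and ended since 0:30. All of this stands. A reader might infer that nothing is checked, that short reactions are lost, or that the AE secondary endpoints are biased; the documents support none of these. What is left is narrower: none of these safeguards is the standardised site assessment. Nor do the PK draws lead staff to the infusion site, since Protocol 4.1.4 and 5.3.2.1 put sampling on the other arm.

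Second, the evidence on time scale comes from another route. The reactions in Protocol 1.2.5 followed SC doses. The AEs named there for IV doses in the Japanese trial include no infusion-site reaction. The single-rising-dose IV trial names one injection site haematoma, without a duration. This stands too, and it rules out any single loss figure. With durations uniform over 0 to 4 h, onset in the half hour after infusion end gives a loss of 2.25 / 4 = 56%. Onset in the half hour after infusion start gives 0.25 / 4 = 6%. Both rest on assumptions.

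Third, local tolerability is one descriptive table and is not in the visible endpoint lists. SAP section 7 separates IV and SC tables unless stated otherwise, and all IV groups share one schedule. This limits the harm: comparison across IV doses is not distorted by different check times, and the IV–SC mismatch matters only if someone sets the two frequencies side by side.

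**Conclusion.** The point holds in a limited form. Flow Chart I.V. has no AE query and no standardised site assessment from 0:30 to 4:00, an interval that contains the last 60 minutes of the infusion and the 2.5 hours after it. A reaction confined to that interval may be missed by the assessment that SAP 7.8.5 tabulates, although it may still be recorded as an AE. The IV local tolerability frequency can therefore err low, and its timing does not match SC.

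The size of the loss cannot be fixed from the documents. With onset in the half hour after infusion end, scheduled capture goes from 0% at durations up to 2 h to 100% at 2.5 h or more.

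The matching marks may suggest that the SC column was carried over unchanged. The re-timed PK sample makes that plausible, but the documents do not say so and the point does not depend on it. This is a cheap improvement to structured safety data. The primary PK endpoints are unaffected.

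**What to change.** In the Day 1 rows of Flow Chart I.V., add an AE-query mark with footnote 5 at 1:30, after the end-of-infusion PK sample that footnote 9 puts first, or at 2:00. Staff already take PK, ECG and vital signs at both. The two times are not equivalent: 1:30 picks up reactions present as the infusion ends, and 2:00 picks up those arising in the half hour after it.

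Keep the 0:30 mark. Moving it instead of adding one would remove the only scheduled AE query and site check during the infusion. Leave the SC chart unchanged.

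The cost is one chart mark, one eCRF time point and a brief inspection. A few more mild, transient findings will be recorded. If IV dosing is already complete, state the timing limitation in the clinical trial report and do not compare IV with SC local tolerability frequencies.
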